Objectives:	
Primary:
 
 1) Characterize the PK of metronidazole and its metabolite 2-hydroxymetronidazole in the plasma and intestinal wall of healthy infants undergoing intestinal surgeries 
Secondary:
 
 1) Characterize the contribution of intestinal CYP2A6 metabolism on metronidazole
Study Design:	Prospective, single center, open-label, PK study
Study Population:	Children \leq 2 years of age undergoing intestinal surgery
Number of Participants:	Up to 20
Number of Sites:	1
Duration of Participant Participation:	Day of surgery. Remote monitoring of patient record for 30 days postoperatively
Dose Schedule:	Per routine medical care
Estimated Start:	May 2020
Estimated Time to Complete Enrollment:	18 months
Inclusion Criteria	
 1) Age 0 to \leq 2 years at enrollment 2) Written informed consent provided by a parent or legal guardian 3) Scheduled to undergo elective intestinal operation for the removal of non-infected bowel 4) Sufficient intravascular access to complete the study procedures
Exclusion Criteria:	
 1) Prior treatment with metronidazole for any dose during the 72 hours prior to study drug administration. 2) Patients with active inflammatory or infectious conditions of the bowel such as inflammatory bowel disease, Hirschprung's disease in the portion of bowel to be excised, diverticular disease, cancerous or pre-cancerous lesions, colitis, enteritis, ulcerative disease, Meckel's diverticulum, celiac disease, and irritable bowel syndrome. 3) Renal dysfunction defined as serum creatinine >2 mg/dL at enrollment

	
4) Receiving any extracorporeal life support including extracorporeal membrane oxygenation, ventricular assist devices, and renal replacement therapy at enrollment5) Any condition or circumstance that, in the opinion of the investigator, would compromise the safety of the participant or the quality of the data.
--	---

Table 1. Schedule of Study Procedures

Assessments	Screening Period Day -30 to 0	Treatment Period Operative Day, Day 1	Postoperative Period Day 2 to Day 31
Informed consent/assent	X		
Demographics ^a	X		
Clinical data ^b			
Medical history	X		
Physical examination	X	X	
Height/length and body weight	X	X	
Vital signs ^c	X	X	
Clinical laboratory parameters ^d	X	X	
Serum creatinine	X	X	
Study drug administration		X	
Events of Special Interest ^e		X	X
Adverse Events ^f	X	X	X
Intraoperative Complications ^g		X	
Postoperative Complications ^g		X	X
Prior and Concomitant therapy	X	X	
Pharmacokinetic data			
PK sample collection			
Plasma sample collection		X	
Intestine sample collection		X	

a: Demographics to be included: gender, date of birth, age, race, comorbidities, gestational age at birth and birth weight

b: May be obtained through review of electronic medical record. All assessment or laboratory collections performed as standard of care only. No assessments or blood draws other than PK data are performed solely for the purposes of this study

c: Vital signs to be included: weight, height, heart rate, respiratory rate, oxygen saturation, and blood pressure

d: Clinical laboratory parameters to be included: WBC, Hg, HCT, Plt, PT, PTT, BUN, serum creatinine, potassium, sodium, AST, ALT, total bilirubin, albumin, prealbumin, ESR, CRP, any blood, tissue, urine cultures as obtained per standard of care

e: Events of Special Interest include: gastrointestinal surgeries, sepsis, wound infection, urinary tract infection, feeding intolerance, transfusion requirements, phlebotomy complications

f: Adverse events related to study procedures (ie phlebotomy)

g: Complications will be assessed through the electronic medical record including excessive blood loss, transfusion requirements, injury to any organ system, infection in any organ system including wound bed, unanticipated return to the operating room, and any unexpected intra- or postoperative occurrence that requires medical or surgical attention

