6 STUDY PROCEDURES

6.1 Screening

Study procedures and their timing are summarized in the SoA. Protocol waivers or exemptions are not allowed unless approved by the study PI and IRB. Immediate safety concerns should be discussed with the PI immediately upon occurrence or awareness to determine if the participant should continue or discontinue study intervention. Adherence to the study design requirements, including those specified in the SoA, is essential and required for study conduct.

All screening evaluations must be completed and reviewed to confirm that potential participants meet all eligibility criteria. The investigator will maintain a screening log of consented patients to record details of all participants screened and to confirm eligibility or record reasons for screen failure, as applicable. Procedures conducted as part of the participant's routine preoperative management (eg, blood count, creatinine) and obtained before signing of the ICF may be used for screening or baseline purposes provided the procedures meet the protocol-specified criteria and are performed within the time frame defined in the SoA. If a patient does not have desired laboratory values, they will be obtained through standard of care measurements as able, most often occurring during preoperative visits to either surgery or anesthesia, in hospital consultations to surgery, or in the standard of care preoperative laboratory collection on the day of surgery.

This study will consist of a Screening, Treatment, and Postoperative Period.

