6.6 Laboratory Evaluations

6.6.1 Clinical Laboratory Evaluations

For all time points, the following labs may be recorded while the patient is on study if collected per standard of care.

1. Any serum chemistry values obtained during perioperative visits prior to or on the day of surgery and during duration any postoperative stay. These include: WBC, Hg, HCT, Plt, PT, PTT, BUN, serum creatinine, potassium, sodium, AST, ALT, total bilirubin, albumin, prealbumin, ESR, CRP. If multiple values for a laboratory are obtained in the pre- or post-operative period, the values recorded will be the value closest to the day of surgery.

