6.7 Concomitant medications

The name, daily dose, and date of administration of each concomitant medication of interest will be recorded for all doses given from day of surgery until the end of the study. Medications of interest include:

- Other systemic antimicrobials
- Oral anticoagulants
- Inducers of CYP 2A6:
 - Rifampicin
 - Barbiturates such as amobarbital, pentobarbital, phenobarbital and secobarbital
- Inhibitors of CYP 2A6 such as:
 - Amiodarone
 - Amlodipine
 - Buprenorphine
 - Clofibrate
 - Clotrimazole
 - Desipramine
 - Disulfiram
 - Entacapone
 - Fenofibrate
 - Gabapentin,
 - Isoniazid
 - Ketoconazole
 - Letrozole
 - Methimazole
 - Methoxsalen

- Metyrapone
- Miconazole
- Modafinil
- Orphenadrine
- Pilocarpine
- Selegiline
- Sulconazole
- Tioconazole
- Tranylcypromine

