9 CLINICAL MONITORING

This study does not provide intervention to the patient that has the potential to cause harm. Enrolled patients are receiving metronidazole as part of their treatment plan. However, the study will collect information regarding the presence of harmful clinical events that occur as a result of metronidazole infusion.

The electronic medical record will be searched for blood, urine, and tissue cultures in the postoperative period to monitor for infectious complications and noted in the CRF.

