10.2 Analysis Plan

Population for Analysis

All enrolled participants with at least 1 evaluable PK sample will be included in the PK analysis and all participants who receive at least 1 dose of study metronidazole will be included in the safety analysis population.

Statistical Methodology

Descriptive statistics, such as number of observations, mean, median, 95% CI, standard deviation, standard error, minimum, and maximum, will be presented by age cohort for continuous variables (such as height, weight, and BMI percentile). Other descriptive statistics, such as counts, proportions, and/or percentages, will be presented by age cohort group to summarize discrete variables (such as race and sex).

Demographics, Baseline Characteristics, and Clinical Course

The number of participants completed and discontinued early from study, and the reasons for discontinuation, will be summarized. Demographic and baseline characteristics will also be summarized. Variables include race, age, sex, ethnicity, and other selected clinical variables will be recorded prior to initiation of study drug. Variables including drug dosing and other selected clinical variables during study drug administration will be recorded.

Safety and Clinical Laboratory Analyses

Laboratory data (serum BUN, serum creatinine, potassium, sodium, AST, ALT, total bilirubin, albumin, prealbumin, ESR, CRP, serum WBC count, Hg, Hct, platelet, PT, PTT) will be tabulated by age cohort. Continuous laboratory measurements will be described using univariable descriptive statistics (mean, median, etc.); observed values and changes from baseline will be summarized. Lab tests reflective of electrolyte abnormalities (e.g., hyponatremia, hypokalemia) will be further summarized in terms of the most extreme values and largest changes from baseline (in the appropriate direction) observed from start of study drug through the end of therapy.

Adverse events and events of special interest will be summarized by age cohort and relationship to drug exposure will be explored. Prior and concomitant medications will be summarized by World Health Organization (WHO) drug class.

PK Analysis

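### Table 1 and the 6.4 postoperative list omit medication and culture data that 6.7 and Section 9 require, and laboratory values that 6.6.1 permits, so the descriptive safety summaries in 10.2 may be incomplete

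*Combined protocol and SAP*

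**What the plan says.** **Schedule.** In Table 1 the rows "Clinical laboratory parameters ^d", serum creatinine and "Prior and Concomitant therapy" carry a mark for Screening (Day -30 to 0) and for Day 1, and none for Day 2 to 31. Footnote d places blood, tissue and urine cultures in the laboratory row. Footnote b says that only PK samples are drawn for the study and that everything else comes from routine care.

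**Status of the schedule.** Section 6.1 describes the schedule as a summary of procedures, then states: "Adherence to the study design requirements, including those specified in the SoA, is essential and required for study conduct".

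**Postoperative list.** Section 6.4 covers adverse events, events of special interest and postoperative complications, including infectious ones. It does not name laboratory values, culture results or medications.

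**Text that goes further.**
- 6.7 records medications of interest "for all doses given from day of surgery until the end of the study".
- Section 9: "The electronic medical record will be searched for blood, urine, and tissue cultures in the postoperative period".
- 6.6.1 says that laboratory values may be recorded from visits "prior to or on the day of surgery and during duration any postoperative stay". Where there are several values in the pre- or postoperative period, it keeps the one nearest to surgery.

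**Timing on Day 1.** Section 6.3 takes laboratory values only where they exist. Section 6.1 says that missing values may be obtained "in the standard of care preoperative laboratory collection on the day of surgery".

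**Analysis.** For continuous laboratory measurements, 10.2 says "observed values and changes from baseline will be summarized". For electrolyte abnormalities it adds the most extreme values and largest changes between the start of study drug and the end of therapy.

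**The concern.** Two parts of the protocol that staff would use as checklists, Table 1 and 6.4, leave out data that other sections ask for. No section says which prevails. Abstraction could then differ between infants, depending on which section was followed.

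Three kinds of data are exposed: postoperative medications of interest (including other systemic antimicrobials), negative postoperative cultures, and laboratory values drawn after the dose. The last matters for interpretation. 10.2 presents change from baseline under safety without defining baseline and without requiring the later value to follow the dose. A difference between two pre-dose values would carry no information about the drug, yet it could appear in a safety table.

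**Working it through.** No sample-size or power figure enters this point. The check is a comparison of sections and a day count.

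**Step 1: schedule and text side by side.**

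| Item | Table 1, Day 2 to 31 | Section 6.4 | Other text | Force of that text |
|---|---|---|---|---|
| Concomitant medications of interest | blank | not named | 6.7: to end of study | required |
| Cultures | blank (footnote d) | only as infectious complications | Section 9: postoperative search | required |
| Laboratory values, creatinine | blank | not named | 6.6.1: postoperative stay | permitted |

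The conflict is firm for medications and cultures and weaker for laboratory values. Creatinine has its own row but also appears in footnote d, so the three blank rows amount to two distinct items: laboratory parameters with cultures, and medications.

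**Step 2: length of the gap.** Day 2 to Day 31 is 31 − 2 + 1 = 30 days, which agrees with the 30-day follow-up in 5.3. From Day 1 to Day 31 there are 31 days, of which the schedule marks 1 and leaves 30 unmarked. The full 30 days apply to 6.7 and to the postoperative period in Section 9. They do not apply to 6.6.1, which reaches only to the end of the postoperative stay, and the documents do not give that length.

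**Step 3: what change from baseline would contain.** Assume that a preoperative draw on Day 1 comes before the metronidazole dose. The documents do not fix this order. For an infant with a screening value, the schedule alone gives:
- Day 1 draw preoperative only: later value minus screening value is pre-dose minus pre-dose.
- Day 1 draw after the dose: the change is post-dose minus pre-dose, as intended.
- No Day 1 draw: no change can be computed.

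If postoperative values are also taken under 6.6.1, the first and third cases can gain a post-dose value where routine care produced one. How many infants fall in each case cannot be derived from the documents.

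**Step 4: the single-value rule.** If 6.6.1 keeps one value per test in the postoperative period, the one nearest to surgery, then the most extreme value available from that period is simply that one value. A later and more abnormal result would not be on file. 10.2 does not define the end of therapy, so whether its window reaches past Day 1 is also open.

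**The case against.** The strongest reply is that a blank cell forbids nothing. Section 6.1 calls the schedule a summary, and its adherence sentence covers all design requirements, with the schedule as one part. On that reading 6.7 and Section 9 bind equally, and staff who follow the whole protocol collect medications and cultures. This stands as far as it goes. A reader might infer that the schedule overrides the text and that the trial will have no post-dose laboratory safety data. The documents do not support that: a Day 1 mark can cover a draw after the dose, and the multiple-values rule in 6.6.1 plainly foresees postoperative values.

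A reader might also infer that infection events become uninterpretable without antimicrobial records. That is not supported either. The 8.1 definitions of sepsis, wound infection and urinary tract infection rest on clinical-team judgement or culture results, not on antimicrobial records. The Events of Special Interest row is marked for Day 2 to 31, so positive cultures partly surface there. Grade 2 of the postoperative complication scale in 8.3 captures complications that need drug treatment.

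On the laboratory analysis, the extreme-value window in 10.2 opens with the drug, and 10.2 has selected clinical variables recorded before it starts. Neither defines baseline for the change summary or ties the later value to after the dose.

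Finally, laboratory safety is neither an objective nor an outcome measure in Section 3, and no mark can guarantee a value that routine care does not produce. Both are true, and both limit the weight of the point. What remains is that Table 1 and 6.4 omit items that 6.7 and Section 9 require.

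**Conclusion.** The conflict holds, at the level of something that should be corrected. It is firm for concomitant medications (6.7) and for the culture search (Section 9), and partial for laboratory values, which 6.6.1 permits but does not require. Staff who work from Table 1 and 6.4 could miss postoperative medications, negative cultures and post-dose laboratory values. In some infants the reported change from baseline could be a difference between two pre-dose values.

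The reach is modest: descriptive safety summaries in a single-centre study of up to 20 infants. The PK objectives do not depend on it. The documents do not show that safety data will be lost, only that the schedule and 6.4 do not secure their collection.

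The conclusion rests on two assumptions. The first is that the blank cells in Table 1 are blank in the source. Neighbouring rows keep their postoperative marks, so the placement looks reliable. The second is that the preoperative draw on Day 1 precedes the dose.

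**What to change.** 1. In Table 1, mark the postoperative column for laboratory parameters (with cultures and creatinine) as collected where routine care produces them, and mark concomitant medications of interest to match 6.7.
2. Add the same items to the list in 6.4.
3. Record the draw time of each laboratory value from the medical record.
4. In 10.2, define baseline as the last value before the metronidazole infusion, and compute change only to values drawn after it.
5. Reconcile the nearest-to-surgery rule in 6.6.1 with the extreme-value summary in 10.2. Either abstract all values in the analysis window or drop that summary. In the same edit, state what the end of therapy means.

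The cost is a few table marks, short edits to 6.4, 6.6.1 and 10.2, a draw-time field on the case report form and somewhat more chart abstraction. The change summary will have a smaller n, because infants without a post-dose value drop out of it. No new blood draws are needed.

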2 BACKGROUND INFORMATION AND RATIONALE

2.1 Background Information

2.1.1 Complicated Intra-Abdominal Infections

Complicated intra-abdominal infections (cIAI) are a leading cause of infant morbidity and mortality. Up to 14% of high-risk infants develop cIAI¹, and up to 30% of those affected die². Common infantile cIAIs involve bowel necrosis or perforation from necrotizing enterocolitis, Hirschsprung disease, gastroschisis, or omphalocele. Bacterial translocation from intestinal lumen into the intestinal wall is a key pathophysiologic component of cIAI³.

2.1.2 Current Antibiotic Practice

Current antibiotic regimens for cIAI are derived to achieve bactericidal plasma concentrations, but whether these dosing regimens result in appropriate antibiotic concentrations in the intestinal wall of infants is unknown⁴⁻⁶. cIAI treatment regimens vary, but multi-agent therapy and coverage against anaerobes including *Bacteroides* and *Clostridium* species is recommended and commonly achieved in infants with metronidazole⁷.

2.1.3 Antibiotic Penetration of the Intestine

Intestinal wall concentrations of antibiotics are essential to treat local bacterial infection and improve outcomes. Failure to reach optimal antibiotic concentrations in the intestinal wall may result in abscess formation, intestinal necrosis, and secondary bacteremia, thus worsening clinical outcomes³. Optimizing intestinal wall concentrations of antibiotics in infants with cIAI is therefore an urgent and unmet public health need. Antibiotic uptake from the blood stream into the intestinal wall and local metabolism determine tissue concentrations, and are complex and understudied processes dependent on perfusion, endothelial integrity, and expression and function of transporters and metabolizing enzymes⁸. These processes are affected by both pathophysiologic alterations of cIAI and by infant growth and maturation⁹. Prior studies attempting to understand this relationship sampled enteric flora or peritoneal fluid, but none directly studied human intestinal tissue¹⁰. These alternate approaches precluded characterization of both intestinal wall absorption and intestinal wall metabolism of metronidazole, the latter occurring primarily via cytochrome P450 (CYP) 2A6.

2.1.4 Metronidazole Metabolism

The primary metabolizing enzyme of metronidazole is CYP2A6 and metronidazole's primary metabolite is 2-hydroxymetronidazole, which can exhibit up to 65% of metronidazole's antimicrobial activity. CYP2A6 exhibits significant ontogeny in liver and oral mucosal tissues, and adult intestinal wall expression is highly variable (CV%>50%). However, ontogeny and interindividual variability of CYP2A6 expression and activity in the intestinal wall of infants are unknown^{11,12}.

2.2 Study Rationale

Our overarching hypothesis is that intestinal wall penetration of metronidazole in infants will vary with age and require optimization of current dosing regimens designed to target plasma exposure only. To test this hypothesis, we will perform an opportunistic PK study of infants receiving perioperative

metronidazole per standard of care at the time of scheduled intestinal resection surgery. Plasma and intestinal wall samples will be collected intra-operatively following administration of metronidazole for measurement of metronidazole and its primary metabolite concentrations in the plasma and the intestinal wall. These data will be used to characterize the pharmacokinetics of metronidazole in plasma and intestinal wall of infants.

2.3 Potential Risks and Benefits

2.3.1 Risk Assessment

Risks of Intestinal Sampling

There are risks to removing the intestine of a patient, however patients enrolled in this study are already undergoing bowel excision for clinical indications described in section 5 in the study design section. A small piece (goal 500mg) of bowel will be taken from the excised portion of bowel, but no additional bowel will be excised for the purpose of this study. Therefore, no additional risk of surgery will be introduced through participation in this study. There will be no discomfort associated with intestinal excision as the patient will be under general anesthesia as per standard of care.

Risks of Blood Drawing

There are risks to blood sampling, usually some pain/discomfort with the blood draw/stick however the patient will be under anesthesia during the time of IV insertion per standard of care for surgery. Every effort will be made to use an already established intravenous line, rather than a new access site. Less than 5mL of blood will be sampled in total, therefore this will not contribute to a clinically significant amount of blood loss.

Risk of Loss of Confidentiality

There is a potential risk of loss of confidentiality. Every effort will be made to protect participants' confidential information, but this cannot be guaranteed. All patients will be assigned a study number and de-identified information will be housed on a Duke RedCAP database with access only granted to study personnel who have had the appropriate training regarding HIPPA compliance and confidentiality.

Unforeseen Risks

There may be other risks to the participant from this research that are not known or foreseeable at this time.

2.3.2 Benefit Assessment

This study will provide pediatric population-specific safety, PK, and preliminary efficacy data for metronidazole administered per standard-of-care in children with cIAI.

